5.3 Concomitant Therapy and Supportive Care Guidelines

It is **preferred** that patients do not receive systemic therapy within 2 weeks of starting and ending SBRT. However, given that select systemic agents are appropriate with concurrent radiation and that some patients may need treatment more urgently, the decision to treat will be at the discretion of the treating radiation and/or medical oncologist.

5.4 Women of Childbearing Potential

Women of childbearing potential (defined as women with regular menses, women with amenorrhea, women with irregular cycles, women using a contraceptive method that precludes withdrawal bleeding, and women who have had a tubal ligation) are required to have a negative serum or urine pregnancy test within 14 days prior to the start of SBRT.

Female and male patients (along with their female partners) are required to use two forms of acceptable contraception, including one barrier method, during SBRT.

If a patient is suspected to be pregnant, SBRT should be immediately discontinued. In addition a positive urine test must be confirmed by a serum pregnancy test. If it is confirmed that the patient is not pregnant, the patient may resume dosing.

If a female patient or female partner of a male patient becomes pregnant during SBRT, the investigator must be notified in order to facilitate outcome follow-up.

5.5 Duration of Therapy

If at any time the constraints of this protocol are considered to be detrimental to the patient's health and/or the patient no longer wishes to continue protocol therapy, the protocol therapy should be discontinued and the reason(s) for discontinuation documented in the case report forms.

In the absence of treatment delays due to adverse events, treatment may continue for a total of 5 fractions of SBRT or until one of the following criteria applies:

- Documented and confirmed disease progression
- Intercurrent illness that prevents further administration of treatment
- Death
- Unacceptable adverse event(s)
- General or specific changes in the patient's condition render the patient unacceptable for further treatment in the judgment of the investigator
- Suspected pregnancy
- Serious non-compliance with the study protocol
- Lost to follow-up
- Patient decides to withdraw from the study
- The Siteman Cancer Center decides to close the study

Patients who prematurely discontinue treatment for any reason will still be followed as indicated in the study calendar.

5.6 Duration of Follow-up

Patients will have a single follow-up visit at 3 months post-end of SBRT.

5.7 Lost to Follow-Up

A participant will be considered lost to follow-up if he or she fails to return for the 3 month follow up visit and is unable to be contacted by the study team.

The following actions must be taken if the participant fails to return to clinic for a required study visit:

- The study team will attempt to contact the participant and reschedule the missed visit within 3 days and counsel the participant on the importance of maintaining the assigned visit schedule and ascertain if the participant wishes to and/or should continue in the study.
- Before a participant is deemed lost to follow-up, the investigator or designee will make every effort to regain contact with the participant (where possible, 3 telephone calls). These contact attempts should be documented in the participant's medical record or study file.
- Should the participant continue to be unreachable, he or she will be considered to have withdrawn from the study with a primary reason of lost to follow-up.

6.0 DOSE DELAYS

No dose delays are expected. If necessary, dose delays may occur on a case-by-case basis following discussion with the PI and will follow institutional standards.

7.0 REGULATORY AND REPORTING REQUIREMENTS

The entities providing oversight of safety and compliance with the protocol require reporting as outlined below. Please refer to Appendix B for definitions and Appendix C for a grid of reporting timelines. All investigators treating patients on this study are responsible for ensuring that serious adverse events (as defined in Appendix B) are reported to the Sponsor-Investigator within an adequate timeframe for the event to be assessed by the Sponsor-Investigator for reporting to HRPO, QASMC, and/or FDA.

Adverse events will be tracked from start of treatment through 3 months post-end of SBRT. All adverse events must be recorded on the toxicity tracking case report form (CRF) with the exception of:

- Baseline adverse events, which shall be recorded on the medical history CRF
- Grade 1 AEs regardless of relatedness
- Grade 2-4 AEs that are unlikely related or definitely not related to treatment

Refer to the data submission schedule in Section 11 for instructions on the collection of AEs in the EDC.

Reporting requirements for Washington University study team may be found in Section 7.1.

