1.7 Risk/Benefit Assessment

1.7.1 Known Potential Risks

The medical risks from participating in this study revolve around exposure to proton radiation and increased time required per treatment to allow for day of plan adaptation. Treatment options for patients enrolled in this study include irradiating with online adaptive stereotactic body radiation treatments (SBRT) over 5 days every day or every other day to a dose of 25-50 Gy. All patients undergoing five fractions or fewer fractions with protons would be evaluated for eligibility for this study during a twice weekly proton triage meeting. Patients enrolled in this study would be deemed appropriate for non-adaptive proton SBRT by the treating radiation oncologist.

Adaptive radiation planning enables improved target coverage by accounting for daily changes in anatomy. This results in a higher integrated dose to the tumor, which has the potential of increased radiation toxicity. However, similar studies of photon based radiation adapted planning have shown this approach to be safe, with comparable levels of acute toxicity seen in both adapted and non-adapted conventional plans.

With online adaptation radiation treatment plans, the time a patient spends lying on treatment table may be extended (45-90 minutes) compared to non-adapted conventional plans (20-30 minutes).

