2.0 OBJECTIVES AND ENDPOINTS

Objectives	Endpoints
Primary	
To assess the feasibility of online proton adaptive radiotherapy based on successful delivery of more than 70% of attempted fractions where treatment adaptation is indicated.	
Successful completion of online adaptive proton radiotherapy workflow through treatment delivery in at least 70% of planned adaptive fractions.
 
Success will be defined as PARTy plan creation and delivery of the fraction using the study workflow in one on-table attempt. Unsuccessful planning and workflow delivery will be defined as multiple attempts of the PARTy workflow for one treatment fraction without treatment delivery such that the study workflow is abandoned.

Secondary	
1. To assess the safety of online proton adaptive radiotherapy.	1. Grade 2+ radiation-related toxicity at 3 months as measured by CTCAE v5.0.
Exploratory	

 To assess patient tolerability and satisfaction with online proton adaptive radiotherapy process. To assess dosimetric differences for target coverage and organ at risk (OAR) sparing between adaptive and non-adaptive proton therapy. 	
 Patient reported experience measures (PREMs). Dosimetry evaluation and comparison to non-adapted pre-plan.

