7.2 Exceptions to Expedited Reporting

Events that do not require expedited reporting as described in Section 7.1 include:

- planned hospitalizations
- hospitalizations < 24 hours
- respite care
- events related to disease progression

Events that do not require expedited reporting must still be captured in the EDC.

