9.0 DATA AND SAFETY MONITORING

In compliance with the Washington University Institutional Data and Safety Monitoring Plan, the Principal Investigator will provide a Data and Safety Monitoring (DSM) report to the Washington University Quality Assurance and Safety Monitoring Committee (QASMC) semi-annually. The first report is required either 30 days after the enrollment of the 5th participant (if sooner than 6 months after study activation) or 6 months after study activation (provided at least one patient has been enrolled; if zero patients have been enrolled at the 6-month mark, the first report will be required one year after accrual opens provided at least one patient has been enrolled).

The Principal Investigator will review all patient data at least every six months, and provide a semi-annual report to the QASMC. This report will include:

- Study demographic information (local protocol number, protocol title, list of primary study team members, study sites, primary and secondary sponsors, IND/IDE status, date of most recent QA audit, and study status and history (including activation and suspension dates))
- Accrual information, including study-wide target accrual and actual accrual, anticipated and/or actual accrual end date, and accrual by year by site (if applicable)
- Subject status information presented in both cumulative format (total number of subjects who consented, enrolled, screen failed, started intervention, discontinued intervention, went off study, expired) and current format (number of subjects in screening, on intervention, in follow-up, or off study at time of report)
- Protocol objectives and the number of participants who are evaluable for each objective
- History of study (including summaries of substantive amendments, accrual suspensions and reasons, protocol exceptions, errors, and breaches of confidentiality)
- Summary of exceptions, noncompliance reports, and unanticipated problems reported to the IRB
- Early stopping rules and data describing whether the stopping rules have been met (if applicable)

- Interim analysis plans and the results of the interim analysis (if applicable)
- Separate SAE and worst grade toxicity tables, each separated by site (if applicable) and arm/cohort/dose level (if applicable)
- Participant-level response and survival data by arm/cohort/dose level (if applicable)
- Summary of specimen collection (percentage of participants who have had specimens collected at each required time point)

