APPENDIX E: Patient Reported Experience Measures (PREM) Form

Date of administration: _____ Patient ID: _____ HRPO: _____

Patient reports (1) not at all satisfied, (2) slightly satisfied, (3) moderately satisfied, or (4) very satisfied for the following procedures:				
Interval consult to treatment start	1	2	3	4
Treatment start to treatment completion	1	2	3	4
Treatment duration	1	2	3	4
Overall satisfaction with workflow	1	2	3	4

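### The toxicity form's relatedness filter conflicts with Section 7.2, and non-radiation harm from the longer table time lies outside the safety endpoint

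*Combined protocol and SAP*

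**What the plan says.** **What is recorded.** Section 7.0 sends adverse events to the toxicity CRF with three exceptions: baseline events (which go to the medical history form), "Grade 1 AEs regardless of relatedness", and "Grade 2-4 AEs that are unlikely related or definitely not related to treatment". Serious events are not carved out of the last exception. Section 8.1 adopts the same exceptions by cross-reference.

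**What else must be captured or tabulated.** Section 7.2 lists examples that need no expedited report, including planned hospitalizations and progression-related events, and adds: "Events that do not require expedited reporting must still be captured in the EDC". Section 9.0 requires "Separate SAE and worst grade toxicity tables" in the semi-annual report. Appendix C routes AEs and SAEs that need no expedited report to the monitoring committee through the toxicity table of that report.

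**What the safety endpoint counts.** The secondary objective in Section 2.0 is "To assess the safety of online proton adaptive radiotherapy". Its endpoint is "Grade 2+ radiation-related toxicity at 3 months as measured by CTCAE v5.0". Section 11.2 has the same restriction to radiation-related events.

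**What risks are named.** Section 1.7.1 gives two: proton exposure and the longer time per treatment. On the second it says that "the time a patient spends lying on treatment table may be extended (45-90 minutes) compared to non-adapted conventional plans (20-30 minutes").

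**What patients are asked.** An exploratory objective covers tolerability as well as satisfaction. The form in Appendix E has four items, all on a four-point satisfaction scale. One concerns treatment duration and another is "Overall satisfaction with workflow".

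**The concern.** Two separate matters meet here.

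The first is capture. When relatedness decides whether an event is entered at all, the judgement cannot be checked later from that form. There is no control arm, and Appendix D confirms that there is no interim toxicity analysis and no stopping rule, so the AE record carries most of the safety evidence. Site staff also face two instructions that do not fit together.

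The second is scope. Enrolled patients are already considered suitable for non-adaptive proton SBRT, and Section 11.4 describes dose and fractionation as standard apart from the adaptation. Longer table time is therefore part of what the study adds, yet harm from it that is not radiation injury has no place in the endpoint. Section 11.4 makes the case for wider study conditional on safety being maintained, so a reader will want the safety summary to cover both named risks.

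**Working it through.** The plan states no computed figure on this point, and Section 11.3 says that the sample size is not based on power. The check is therefore mainly a comparison of sections, with some arithmetic on size.

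**1. Following one event through the rules.** Take a grade 3 serious event attributed to disease progression and judged unrelated to treatment.
- Section 7.0: not entered on the toxicity form. It is still notified to the Sponsor-Investigator, because SAE notification has no relatedness condition.
- Section 7.2: exempt from expedited reporting, but must be in the EDC.
- Section 8.0: the CRF list has a toxicity form, a death form and a MedWatch form, but no SAE form. The MedWatch line refers back to Section 7.0.
- Appendix C and Section 9.0: it should reach the committee through the toxicity and SAE tables.

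No listed form clearly takes this event from notification to those tables. In addition, Section 7.0 points to Section 11 for the data submission schedule, which is in Section 8.

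**2. Direction of the error.** An event wrongly called related is on the form and can be re-reviewed. One wrongly called unrelated at grade 2-4 is not. The errors that cannot be corrected from the form are thus all downward.

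**3. Size per patient.** With 10 evaluable patients (Section 11.3), one patient is 1/10 = 10 percentage points. The shift occurs only if the misattributed event is that patient's sole qualifying event; otherwise it is zero.

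**4. Extra table time (Section 1.7.1; five fractions, Section 5.0).**
- Smallest: 45 − 30 = 15 minutes per fraction; × 5 = 75 minutes.
- Largest: 90 − 20 = 70 minutes per fraction; × 5 = 350 minutes.
- Range midpoints: 67.5 − 25 = 42.5 minutes per fraction; × 5 = 212.5 minutes.

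The largest figure pairs the longest adaptive session with the shortest conventional one. These figures measure exposure, not harm.

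**5. Illustration of the filter.** Assumptions that are not in the documents: a true per-patient rate p of grade 2-4 table-time harm, a share s of it judged at least possibly related to treatment, and independence between patients. The chance that at least one of 10 patients has an entry on the toxicity form is 1 − (1 − ps)^10.

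| p | s = 1 | s = 0.5 | s = 0.25 | s = 0 |
|---|---|---|---|---|
| 10% | 65% | 40% | 22% | 0 |
| 20% | 89% | 65% | 40% | 0 |
| 30% | 97% | 80% | 54% | 0 |

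Recording regardless of attribution gives the s = 1 column. Under the present endpoint, harm of this kind that is not radiation-related contributes zero whatever s is.

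**6. Limit of any fix.** With complete capture, 0 events in 10 still leaves an exact upper 95% bound of 1 − 0.05^(1/10) = 25.9% one-sided, or 1 − 0.025^(1/10) = 30.8% two-sided. Better capture widens what is covered; it does not make 10 patients precise.

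**The case against.** The strongest reply is that filtering by relatedness is a deliberate choice for a small descriptive pilot, with a rationale given in Section 11.4, and that no safety threshold depends on the rate. That stands, and it keeps this a matter of improvement except for the conflict between Sections 7.0 and 7.2. Even that conflict can be read narrowly, since 7.0 governs one form and 7.2 speaks of the EDC. But 8.0 lists no other form that plainly takes these events, so the wording still needs settling.

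The reply also disposes of several stronger readings that a reader might infer:
- *That adverse events are discarded.* Grade 5 events, grade 2-4 events at least possibly related, SAE notifications and unanticipated-problem reports are all kept.
- *That the risk of the workflow goes unmeasured.* The filter is relatedness to treatment, not to radiation, so a grade 2+ positioning injury attributed to the session would be recorded. Section 1.7.1 also mentions a higher integrated tumour dose, and toxicity from that is inside the endpoint. A fraction that the patient cannot complete cannot count as a success under Section 11.1, and Section 5.5 has reasons for discontinuation documented.
- *That the treating team makes the attribution.* Appendix B gives the source of the definitions and names no one.
- *That the SAE tables will be incomplete.* Section 9.0 says that the standard tables come from OnCore and does not tie them to the toxicity form. An unclear path is all that can be shown.
- *That Section 8.1 conflicts with 7.0.* It adopts the exceptions in 7.0 expressly.
- *That patients are asked nothing about time.* The PREM item on treatment duration is an indirect signal, although it does not say whether session or course is meant.

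**Conclusion.** The point holds as an inexpensive improvement with one internal contradiction. Sections 7.0 and 7.2 give conflicting instructions on unrelated events that need no expedited report, and serious ones among them lack a clear path into the monitoring tables. The filter also prevents later re-attribution from the toxicity form.

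Separately, non-radiation harm from longer table time is outside the safety endpoint even when it is recorded as treatment-related, and tolerability is assessed only through satisfaction items. A zero on the endpoint could not be read as absence of such harm.

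The effect on the reported rate is bounded as in step 3 of the working. Whether any downward shift would occur is unknown, because the documents give no rate of table-time harm and no rate of misattribution; the percentages in step 5 rest wholly on assumed values.

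**What to change.** 1. In Sections 7.0 and 8.1, record all grade 2+ AEs and all SAEs whatever their attribution. Give the form two attribution fields: radiation, and adaptive workflow (for example prolonged positioning or repeat imaging).
2. In Sections 11.2 and 11.4, keep the present endpoint and add two counts, so that patients with at least one grade 2+ event are reported as any-cause, radiation-related and workflow-related. The any-cause count will include disease-related events and should be labelled so.
3. Reconcile Section 7.0 with Section 7.2, Section 9.0 and Appendix C: state which form holds SAEs that need no expedited report and which table they feed. Correct the pointer from Section 7.0 to the data submission schedule.
4. Optionally, add one line to Appendix E on discomfort from time on the table, and state whether the treatment duration item means the session or the course.

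The cost is a few more CRF entries in 10 patients, a second attribution field, possibly one questionnaire line, and an IRB amendment. The sample size and the primary endpoint do not change.

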7.1 WU PI Reporting Requirements

7.1.1 Reporting to the Human Research Protection Office (HRPO) at Washington University

Reporting will be conducted in accordance with Washington University IRB Policies.

Pre-approval of all protocol exceptions must be obtained prior to implementing the change.

7.1.2 Reporting to the Quality Assurance and Safety Monitoring Committee (QASMC) at Washington University

The PI (or designee) is required to notify the QASMC of any unanticipated problems involving risks to participants or others occurring at WU or any BJH or SLCH institution that has been reported to and acknowledged by HRPO. (Unanticipated problems reported to HRPO and withdrawn during the review process need not be reported to QASMC.)

QASMC must be notified within **10 days** of receipt of IRB acknowledgment via email to [contact]. Submission to QASMC must include the myIRB form and any supporting documentation sent with the form.

7.2 Exceptions to Expedited Reporting

Events that do not require expedited reporting as described in Section 7.1 include:

- planned hospitalizations
- hospitalizations < 24 hours
- respite care
- events related to disease progression

Events that do not require expedited reporting must still be captured in the EDC.

8.0 DATA SUBMISSION SCHEDULE

Case report forms with appropriate source documentation will be completed according to the schedule listed in this section.

Case Report Form	Submission Schedule
Original Consent Form	Prior to registration
On-Study Form Medical History Form	Prior to starting treatment
Toxicity Form	Continuous
Treatment Summary Form	Completion of treatment

PREM Form	Completion of treatment
Follow Up Form	At 3 mos follow-up
Death Form	Time of death
MedWatch Form	See Section 7.0 for reporting requirements

8.1 Adverse Event Collection in the Case Report Forms

All adverse events that occur beginning with start of treatment (minus exceptions defined in Section 7.0) must be captured in the Toxicity Form. Baseline AEs should be captured on the Medical History Form.

Participant death due to disease progression should be reported on the Toxicity Form as grade 5 disease progression. If death is due to an AE (e.g. cardiac disorders: cardiac arrest), report as a grade 5 event under that AE. Participant death must also be recorded on the Death Form.

9.0 DATA AND SAFETY MONITORING

In compliance with the Washington University Institutional Data and Safety Monitoring Plan, the Principal Investigator will provide a Data and Safety Monitoring (DSM) report to the Washington University Quality Assurance and Safety Monitoring Committee (QASMC) semi-annually. The first report is required either 30 days after the enrollment of the 5th participant (if sooner than 6 months after study activation) or 6 months after study activation (provided at least one patient has been enrolled; if zero patients have been enrolled at the 6-month mark, the first report will be required one year after accrual opens provided at least one patient has been enrolled).

The Principal Investigator will review all patient data at least every six months, and provide a semi-annual report to the QASMC. This report will include:

- Study demographic information (local protocol number, protocol title, list of primary study team members, study sites, primary and secondary sponsors, IND/IDE status, date of most recent QA audit, and study status and history (including activation and suspension dates))
- Accrual information, including study-wide target accrual and actual accrual, anticipated and/or actual accrual end date, and accrual by year by site (if applicable)
- Subject status information presented in both cumulative format (total number of subjects who consented, enrolled, screen failed, started intervention, discontinued intervention, went off study, expired) and current format (number of subjects in screening, on intervention, in follow-up, or off study at time of report)
- Protocol objectives and the number of participants who are evaluable for each objective
- History of study (including summaries of substantive amendments, accrual suspensions and reasons, protocol exceptions, errors, and breaches of confidentiality)
- Summary of exceptions, noncompliance reports, and unanticipated problems reported to the IRB
- Early stopping rules and data describing whether the stopping rules have been met (if applicable)

- Interim analysis plans and the results of the interim analysis (if applicable)
- Separate SAE and worst grade toxicity tables, each separated by site (if applicable) and arm/cohort/dose level (if applicable)
- Participant-level response and survival data by arm/cohort/dose level (if applicable)
- Summary of specimen collection (percentage of participants who have had specimens collected at each required time point)
- Abstract submissions/publications
- Summary of any recent literature that may affect the safety of participants or the ethics of the study

Standardized DSM report tables are generated out of OnCore; study-specific DSM report tables are located in Appendix D.

